### **9.2 Secondary Efficacy Analyses**

- The incidence of desensitisation to peanut in the waiting list group after receiving the active intervention (end of phase 2) will be reported and compared with the incidence of desensitisation to peanut in the intervention group (end of phase 1) using Fishers exact test.

- Incidence of response to treatment (i.e. desensitisation to the maintenance immunotherapy dose of 800mg) will be compared between the intervention and waiting list groups using Fishers exact test. Multiple logistic regression will be used to adjust the odds ratio of response to treatment for baseline characteristics described in section 7.2.
- The absolute and fold change in threshold will be compared within and between groups using paired and independent sample t-tests respectively. This may be extended to a linear regression adjusting for baseline covariates (section 7.2)
- QoL scores at the end of phase 1 will be compared between groups using a Mann Whitney U test.
- Change in QoL scores before and after intervention in both groups (Intervention: Phase1 – baseline; Waiting list: Phase 2– Phase 1) will be investigated within groups using a Wilcoxon sign rank test and then between groups using a Mann –Whitney U test.
- Change in peanut IgE from baseline to end of phase 1 will be compared between groups using a Mann–Whitney U test.
- Change in AUC (CD63MFI and %CD63 positive cells) of Basophil histamine release from baseline to end of phase 1 will be compared between groups using a Mann–Whitney U test
- Change in SPT results (peanut and other nuts) from baseline to end of phase 1 will be compared between groups using a Mann– Whitney U test
- Change in WAO score from baseline to end of phase 1 will be compared between groups using a Mann – Whitney U test

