### 4.2.2 Secondary Endpoints

- Incidence of desensitisation to peanut in waiting list patients after receiving the active intervention (end of phase 2)
- Incidence of response to treatment(end of phase 1 (intervention group) and end of phase 2 (waiting list group))
- Fold and absolute increase in threshold (maximum tolerated peanut protein (mg))
- Change in quality of life (QoL) scores from baseline to the end of phase 1
- Change in QoL scores before and after immunotherapy (Baseline to phase 1(intervention group) or phase 1 to phase 2 (waiting list group).
- Change in immunological outcomes (Basophil histamine release, Peanut IgE, Total IgE, and skin prick test diameter (SPT))
- Change in severity of symptoms (World Allergy Organisation (WAO) score) from baseline to the end of phase 1

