## 4.3 Derived variables

- Desensitisation to peanut – able to ingest 1400mg peanut protein without reacting
- Response to treatment – able to ingest 800mg protein without reacting, after immunotherapy

[figure not shown]

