## 5 Study Methods

### 5.1 General Study Design and Plan

Single centre, randomized controlled trial of a novel active intervention (peanut oral immunotherapy) versus the status quo (peanut avoidance) in patients with peanut allergy. Two phase (package) design.

- Phase 1: Subjects randomly allocated (using minimisation methods – 80% chance of being assigned to imbalance minimising arm) to active intervention arm or waiting list arm. After 6 months all patients will be assessed for peanut allergy.
- Phase 2: Participants in waiting list arm still allergic to peanut at the end of phase 1 will be given the active intervention.

The figure below shows the study design.

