## 6 Sample Size

Based on Fisher's exact test with 90% power and 5% significance (two-sided) a sample size of 49 in each group is sufficient to detect proportions of participants with desensitisation to peanut of 64% and 30% in the intervention and control group respectively. Allowing for 5% drop out increases the sample size to 52 participants in each group and 104 subjects overall.

Based on the above we would expect 35 waiting list group patients to proceed to the active intervention in phase 2. To confirm efficacy of immunotherapy the success rate of all participants (intervention and phase 2 waiting list) should be within 10% of the success rate seen in intervention participants alone in phase 1.

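### Section 9.2 tests phase 2 waiting-list results against phase 1 intervention results, a non-randomised treated-versus-treated comparison, and specifies no randomised 6-month comparison at 800 mg

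*SAP*

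**What the plan says.** **Desensitisation after phase 2.** The first bullet of SAP Section 9.2 reports the waiting-list incidence at the end of phase 2 and has it "compared with the incidence of desensitisation to peanut in the intervention group (end of phase 1) using Fishers exact test".

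**Response at 800 mg.** The next bullet reads: "Incidence of response to treatment (i.e. desensitisation to the maintenance immunotherapy dose of 800mg) will be compared between the intervention and waiting list groups". It names Fisher's exact test and an adjusted odds ratio from logistic regression, but no time point. Three other places bear on the timing:
- Section 4.2.2 measures response at "end of phase 1 (intervention group) and end of phase 2 (waiting list group").
- Section 4.3 defines response as "able to ingest 800mg protein without reacting, after immunotherapy".
- Table 2.8 (Section 13.1), the only table for this endpoint, is restricted to patients who had immunotherapy. It uses 6 months for the intervention arm and 12 months for the waiting list, with treatment group among the covariates.

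**Who enters phase 2.** Section 5.1 says: "Participants in waiting list arm still allergic to peanut at the end of phase 1 will be given the active intervention". The footnote to the visit schedule in Section 5.4 likewise limits phase 2 immunotherapy to waiting-list patients not desensitised after 24 weeks.

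**Analysis basis.** Section 9 states that every analysis is by intention to treat and that each test comes with an effect size and a 95% confidence interval.

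**The concern.** A comparison of a treated arm with a later-treated arm contains no treated-versus-untreated contrast. If immunotherapy works equally well in both, a null result is the expected outcome, so the test does not address efficacy. It is not protected by randomisation either: the intervention arm is taken whole, while the phase 2 group is what remains of the waiting list after those no longer allergic at 24 weeks have been removed. The ITT label does not fit that group.

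What is at stake is a secondary endpoint that the design could support properly. Section 5.1 has all patients assessed for peanut allergy after 6 months. That challenge yields a threshold, so tolerance of 800 mg can be derived in both randomised arms. As the plan is worded, that comparison is not specified. A p-value from the cross-phase test could be taken as evidence of similar efficacy, or of a difference, when it establishes neither.

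**Working it through.** **1. Inputs.** Section 6 gives "90% power and 5% significance (two-sided) a sample size of 49 in each group is sufficient". The test there is Fisher's exact test, and the assumed 6-month rates are 64% on intervention and 30% on control. With 5% dropout the plan arrives at 52 per arm, 104 in total. It expects 35 waiting-list patients to enter phase 2.

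**2. The plan's own figures reproduce.**
- The two-proportion formula with continuity correction gives 49 per group.
- Exact Fisher power, enumerated over all tables at 49 v 49 with 64% v 30%, is 0.906.
- 49/0.95 = 51.6, rounded up to 52 per group and 104 overall.
- Phase 2 entrants: 0.70 × 49 = 34.3 and 0.70 × 52 = 36.4, consistent with 35.

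**3. Timing of the two tests, side by side.**

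| Endpoint | Intervention arm | Waiting list | Source |
|---|---|---|---|
| Desensitisation, first bullet of 9.2 | End of phase 1, treated | End of phase 2, treated, selected | Stated in 9.2 |
| Response at 800 mg, second bullet of 9.2 | End of phase 1, treated | End of phase 2, treated, selected | Not stated in 9.2; from 4.2.2, 4.3 and Table 2.8 |

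Under Section 4.3 an untreated waiting-list participant at 6 months has had no immunotherapy, so cannot count as a responder whatever dose is tolerated. No table in Section 13.1 sets out a 6-month between-arm comparison at 800 mg.

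**4. Behaviour of the cross-phase test** (exact Fisher, two-sided 5%, 49 v 35).
- 64% v 64%: rejects with probability 0.039.
- 64% v 54%: power 0.13.
- 64% v 40%: power 0.57.

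**5. Possible effect of selection.** Let *u* be the 6-month desensitisation rate without treatment. Assume that everyone who would recover untreated would also pass if treated, and that 64% pass on treatment overall. The rate among those still allergic is then (0.64 − *u*)/(1 − *u*).

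| *u* | Rate in still-allergic participants | Shortfall from 64% |
|---|---|---|
| 0% | 64.0% | 0 points |
| 10% | 0.54/0.90 = 60.0% | 4 points |
| 20% | 0.44/0.80 = 55.0% | 9 points |
| 30% (Section 6 value) | 0.34/0.70 = 48.6% | 15 points |

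In the last row the 49 v 35 test has power 0.27. If untreated recovery is unrelated to response on treatment, the shortfall is zero at every *u*. These are 1400 mg planning rates; the SAP gives none for 800 mg.

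**6. Feasibility of a randomised 800 mg comparison** (49 v 49, assumed rates).

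| Control rate | Power at 64% treated | At 70% | At 75% |
|---|---|---|---|
| 30% | 0.91 | 0.98 | 0.99 |
| 40% | 0.61 | 0.82 | 0.93 |

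**The case against.** **The 800 mg bullet can be read differently.** It has no time point, its wording resembles that of the primary test in Section 9.1, and Section 9 declares ITT throughout. Figure 2.7 plots the probability of treatment response in the full analysis population by treatment, which would suit a 6-month randomised comparison. This stands in part. A reader might infer that the plan definitely rules out any randomised 800 mg comparison, and the documents do not support that certainty. They do support a narrower statement: the endpoint list, the definition and the only relevant table all place response after immunotherapy, nothing specifies the 6-month test, and Figure 2.7 is ambiguous. On the generous reading, the bullet contradicts Sections 4.2.2 and 4.3 and Table 2.8, and the population still has to be fixed.

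**The selection effect is uncertain.** This stands. Fifteen points might be read as the expected bias. It is the value at one planning rate under one untested assumption, and it falls to zero under others.

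**The results are not uninterpretable.** This also stands. A reader might infer that neither a significant nor a null result could mean anything. Section 9 requires confidence intervals, Section 9.2 also reports the phase 2 incidence, and Section 6 has a separate criterion for confirming efficacy: success in all participants within 10% of the intervention-arm phase 1 rate. Nothing in the SAP says that non-significance will be taken as equivalence. The criterion and the test are not aligned, however. Read as percentage points, the criterion admits a phase 2 rate down to 40%, since (0.64 × 49 + 0.40 × 35)/84 = 0.54, where the test has 57% power.

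**Package 2 has a legitimate purpose.** Describing success in the waiting list once treated is a stated objective, and a treated-only population suits a predictor analysis such as Table 2.8. The difficulty lies in the formal between-arm tests only.

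**Conclusion.** The point holds in this form. The desensitisation test in the first bullet of Section 9.2 is explicitly treated-versus-treated, compares a whole randomised arm with a selected remainder of the other, and conflicts with the ITT statement. The 800 mg test has the same structure when read with Sections 4.2.2 and 4.3 and Table 2.8; that part is an inference from several places, not an explicit statement in the bullet.

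A null result from the cross-phase test would not show similarity: about 4% rejection under equal rates and about 13% power for a 10-point shortfall, at 64% and 49 v 35. A shortfall of 0 to 15 points could arise from selection under the stated assumption, but the SAP does not allow its true size or direction to be calculated, and nothing here quantifies it at 800 mg.

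The reach is limited to secondary analyses. The primary 1400 mg comparison and the 6-month threshold comparison (Table 2.3) are randomised and unaffected; the latter carries related information on a continuous scale. The change should be made because a randomised contrast is available from a challenge already planned.

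**What to change.** 1. For the between-arm test, define the 800 mg endpoint as tolerating at least 800 mg at the end-of-phase-1 challenge, for all randomised participants, without the condition of having had immunotherapy. Compare the randomised arms at 6 months with Fisher's test and the adjusted logistic model, and add a table for it in Section 13.1.
2. Report phase 2 waiting-list desensitisation and 800 mg response as proportions with exact 95% confidence intervals, together with within-participant change from the end of phase 1.
3. Keep any phase 2 versus phase 1 comparison only if labelled non-randomised and descriptive, as a difference with a confidence interval, and exempt it from the ITT statement in Section 9.
4. Keep Table 2.8 as a predictor analysis in treated patients, and state the population and time point of Figure 2.7.

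The cost is SAP wording and one table shell. No further visits, data or participants are needed.

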### 5.4.1 Important Variable Definitions

- Peanut threshold (mg) – The no observed adverse effect level (NOAEL) – the highest cumulative dose of peanut that does not cause a reaction in a DBPCFC
- The lowest observed adverse effect level (LOAEL) is the lowest cumulative dose that causes a reaction (mg) in a DBPCFC
- Peanut IgE (kU/l 0 –1000) – Specific allergy antibody against peanut protein. Higher titres of IgE antibodies indicates higher probability of clinical allergy
- Basophil histamine release – Donor basophils stimulated in vitro by peanut extract at a range of concentrations. Basophil stimulation is detected by the mean fluorescent intensity of a cell surface marker (CD63). Area under the curve (AUC) of mean fluorescent intensity of CD63 (arbitrary units) and of the %CD63 positive cells against dose of peanut protein in milligrams.
- Tryptase (ng/ml) – a marker of background mast cell activation
- SPT diameter (mm 0–20) – A small amount of purified peanut is pricked on to the skin, and the diameter of the resulting wheal is recorded.

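### Week-24 peanut thresholds are capped at the last challenge dose, but the planned t-tests treat the capped values as exact measurements

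*SAP*

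**What the plan says.** Section 4.2.2 lists the fold and absolute increase in threshold as a secondary endpoint and glosses threshold as the maximum tolerated amount of peanut protein. Section 5.4.1 defines the measured threshold as the NOAEL, "the highest cumulative dose of peanut that does not cause a reaction in a DBPCFC".

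For the analysis, Section 9.2 says: "The absolute and fold change in threshold will be compared within and between groups using paired and independent sample t-tests respectively". It adds that a linear regression on baseline covariates may follow. Table 2.3 in Section 13.1 fixes the output as mean, SD, absolute and fold difference with 95% CI, from a t-test.

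Desensitisation (Section 4.3) means being "able to ingest 1400mg peanut protein without reacting", and Section 6 plans on proportions of "64% and 30% in the intervention and control group respectively". Section 9 allows non-parametric tests or transformations where assumptions fail, and asks for an effect size with a 95% CI alongside each test. No section says how to handle a participant who completes the challenge without reacting, and none states the top challenge dose.

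**The concern.** A participant who passes every step has no LOAEL. Their recorded NOAEL is the last dose given, and the amount they could have tolerated is known only to be at least that. By the plan's own assumptions this could be most of the intervention arm and a sizeable part of the control arm.

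For such a participant the computed change is the top dose minus baseline, or the top dose divided by baseline. Baseline sets the result, not the size of the response. With a 1400 mg top dose, the largest fold change that can be recorded is 1400/5 = 280 from a 5 mg baseline but only 1400/200 = 7 from a 200 mg baseline. (5 mg and 200 mg are cut-points of the challenge-threshold factor in Section 5.3.)

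At stake is how a named secondary endpoint is read. A mean change in capped NOAEL could be reported as the change in maximum tolerated protein, which is a different quantity. The permission in Section 9 does not settle this: a rank test suits the hypothesis test, but neither ranks nor a transformation recover an effect size above the cap.

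**Working it through.** **Inputs from the SAP.** 64% and 30% tolerating 1400 mg, 49 per group, 90% power, two-sided 5%, 5% drop-out (Section 6). Entry requires a positive challenge (Section 5.2.1), so the cap acts on follow-up values, not baseline.

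**Assumptions, not in the SAP.** Top dose 1400 mg; log-normal week-24 thresholds; equal SDs on the log scale. Each is varied below. SDs are in natural-log units.

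**The plan's own figure.** Exact enumeration of Fisher's test at 64% versus 30% gives power 0.896 at 48 per group and 0.906 at 49. Then 49/0.95 = 51.6, rounded up to 52 per group, 104 in all. The stated sample size reproduces. The SAP gives no figure for the threshold analysis.

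**Numbers at the cap.** 0.64 × 49 = 31.4 and 0.30 × 49 = 14.7, so about 31 and 15.

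**Within groups.** A capped value is never above the uncapped one, and baselines are not capped. The mean within-group change is therefore too low as soon as anyone's true threshold exceeds the top dose. This needs no distributional assumption.

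**Between groups, log scale.** Let c be the log top dose, σ the log-SD, and a = (c − mean)/σ, so the proportion passing is 1 − Φ(a). Then E[min(X, c)] = c − σ·g(a), with g(a) = aΦ(a) + φ(a).

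- Intervention, 64% pass: a = −0.3585, g = 0.2451.
- Control, 30% pass: a = 0.5244, g = 0.7148.
- True difference: 0.5244 + 0.3585 = 0.8829 σ.
- Capped difference: 0.7148 − 0.2451 = 0.4697 σ.
- Ratio: 0.4697/0.8829 = 0.532, whatever σ is.

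As geometric fold ratios this is 1.60 observed against 2.42 true at log-SD 1.0, and 2.02 against 3.76 at log-SD 1.5.

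**Lower control rates, intervention held at 64%.**

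| Controls passing | True (σ) | Capped (σ) | Ratio |
|---|---|---|---|
| 30% | 0.883 | 0.470 | 0.53 |
| 15% | 1.395 | 0.869 | 0.62 |
| 5% | 2.003 | 1.421 | 0.71 |
| 1% | 2.685 | 2.085 | 0.78 |

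**Higher top dose (64% versus 30%, equal SDs, log-SD 0.5 to 2.0).** The log-fold shortfall is 8% to 34% at 2800 mg and 0% to 23% at 5600 mg, against 47% at 1400 mg.

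**Unequal SDs (top dose 1400 mg).** With log-SDs of 0.75 and 1.5 in either order, and control rates of 1% to 30%, the log-fold shortfall runs from 12% to 82%.

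**Absolute difference (top dose 1400 mg, 64% versus 30%).** With equal SDs it is 67%, 83% and 93% too small at log-SD 0.5, 1.0 and 1.5. With log-SD 0.75 in the intervention arm and 1.5 in controls it is about unbiased: 477 mg capped against 463 mg true.

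**The test itself (4000 simulated trials, 49 per arm, log-SD 1.0 or 1.5).** Type I error is 0.051 to 0.057. Power is 96.5% capped against 99% uncapped. The capped 95% CI covers the uncapped log difference in about 11% of trials.

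**The case against.** A reader might infer that the planned effects are certainly and strongly understated, that the confidence interval is simply wrong, and that a censored regression should replace the t-tests. The documents do not support this.

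- **Top dose.** 1400 mg is the desensitisation criterion. It is not stated to be the last challenge step, and the dose schedule may sit in the protocol.
- **Distribution.** The SAP gives no SD or shape for the threshold. The 30% control rate is a planning value in participants who all reacted at entry; lower rates give a smaller shortfall. In one unequal-SD case the absolute between-group difference is not understated at all.
- **Estimand.** Section 5.4.1 defines threshold as the observed NOAEL. The mean difference in that bounded quantity is legitimate and the t-test of it is sound. The 11% coverage refers to a latent threshold beyond any dose given.
- **Remedy.** An interval-censored log-normal model does well on data that follow its assumptions, but not if response is bimodal. In simulations with assumed responders near 2000 mg and others near 100 mg, about 63% and 31% passing, one run gave a model fold ratio of 6.7 against a true 2.76 (capped 2.46); a second gave 6.2 against 2.9 (capped 2.6). With few controls passing, the model gave 13.8 against 7.4 (capped 5.7).
- **Existing output.** If 1400 mg is the top dose, Table 2.1 already shows how many reach it, and Figure 2.1 is already a box plot.

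All of this stands. It limits the size of the problem and rules out the stronger remedy. It does not supply a rule for participants who pass, nor turn a capped mean into the change in maximum tolerated protein named in Section 4.2.2.

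**Conclusion.** The point holds in limited form. The SAP analyses a bounded threshold as if it were fully observed, while planning for many participants to reach a dose that may be the bound. Read as the change in maximum tolerated protein, the mean within-group change is too low whenever anyone's true threshold lies above the top dose. The between-group effect can be too small: by 47% on the log-fold scale with a 1400 mg top dose, log-normal thresholds, equal SDs and 64% versus 30% passing, and by 22% to 38% if 1% to 15% of controls pass. With a higher top dose it may be slight; with unequal SDs it can be anywhere from modest to very large.

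The harm is to estimation and interpretation of a secondary endpoint. The hypothesis test on the observed NOAEL is valid, and the primary comparison of desensitisation is untouched. The change is worth making before analysis.

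**What to change.** In Section 9.2 and Table 2.3:

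1. State the top challenge dose, and that a participant who passes it has a threshold known only to be at or above it.
2. Make the main between-group comparison of week-24 threshold and of its change rank-based (Mann-Whitney), with those who pass tied at the top for the threshold itself. Use a signed-rank test within groups. Changes still carry the cap, so the threshold comparison is the cleaner of the two.
3. Report medians and quartiles, written as '≥ top dose' where reached, with the number at the ceiling in each arm.
4. Label any mean absolute or fold change as the change in NOAEL capped at the top dose, and within-group means as lower bounds for the change in maximum tolerated dose.
5. Optionally add an interval-censored regression on the log scale as a sensitivity analysis, with its distributional assumption stated. It should not be the main analysis, because it can substantially overstate the effect if response is bimodal.

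The cost is SAP wording and standard tests, with no new data. The small downside is that a headline mean fold change gives way to a median or a bounded figure.

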## **9 Efficacy Analyses**

All statistical tests described in this section use a 2-sided 5% significance level. Non-parametric tests may be used instead of parametric tests if the assumptions are not appropriate. Sensible transformations of data may be used to allow the data to fulfil assumptions.

Plots (e.g. histograms, residuals) will be used to assess the assumptions and fits of regression models.

Tests will be accompanied with a measure of effect size (e.g. difference, odds ratio etc.) and a 95% confidence interval.

All analyses will be performed on an intention to treat (ITT) basis.

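### The within-group t-test of threshold in SAP 9.2 cannot show efficacy: on the plan's own 30% control rate it would be significant without treatment

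*SAP*

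**What the plan says.** SAP section 9.2, headed as secondary efficacy analyses, plans for the peanut threshold: "The absolute and fold change in threshold will be compared within and between groups using paired and independent sample t-tests respectively". The next sentence allows, but does not require, a linear regression adjusting for baseline covariates. For quality of life (QoL), change before and after intervention "will be investigated within groups using a Wilcoxon sign rank test", followed by a between-group test. Section 9 sets the level for all of them: "All statistical tests described in this section use a 2-sided 5% significance level".

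Section 6 sizes the trial on "proportions of participants with desensitisation to peanut of 64% and 30% in the intervention and control group respectively". It then uses the control rate a second time, as an expectation: "Based on the above we would expect 35 waiting list group patients to proceed to the active intervention in phase 2". Section 5.2.1 requires a positive blinded challenge at entry, section 4.3 defines desensitisation as tolerating 1400 mg, and section 5.4.1 defines threshold as the highest cumulative dose without a reaction (NOAEL).

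In the table list, Table 2.3 covers threshold at baseline and 6 months and compares groups only. Table 2.5 lists both the within-group and between-group QoL tests.

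**The concern.** A paired test asks whether the mean changed. It does not ask whether immunotherapy changed it. The two questions coincide only if nothing would happen without treatment, and the SAP assumes otherwise: nearly a third of the waiting-list arm is expected to go from a positive challenge to tolerating 1400 mg with no immunotherapy. Over baseline to 6 months the waiting-list arm is untreated, so a significant paired test there would reflect natural change, repeat testing and selection on a positive entry challenge. The same forces act in the intervention arm, where the paired test cannot tell them from treatment.

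The QoL signed-rank test has the same design weakness. It has no concurrent control, and section 5.3 states that participants are not blinded to group.

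At stake is how a secondary result is read. A very small p-value reported under an efficacy heading invites a conclusion that the test cannot support.

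**Working it through.** **The plan's own figures.** Fisher's exact test, 64% against 30%, two-sided 5%: enumerating all outcomes gives 90.6% power at 49 per group and 89.6% at 48, so 49 reproduces. Drop-out: 49 / 0.95 = 51.6, rounded up to 52. Phase 2 entrants: 0.7 × 49 = 34.3, or 0.7 × 52 × 0.95 = 34.6, consistent with 35.

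**Inputs for the paired test.** From the SAP: n = 49, untreated rate p = 0.30, target 1400 mg, two-sided 5%. Assumed, because the SAP does not give them: the baseline threshold b, and the change c in participants not desensitised. No participant is taken to tolerate 1400 mg at baseline.

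**Expected result.** A share p rises by 1400 − b and the rest change by c.

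- Mean change = p(1400 − b) + (1 − p)c
- SD = (1400 − b − c) × √[p(1 − p) × n/(n − 1)]
- t = mean / (SD/√n)

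With c = 0 the baseline cancels: t = √[(n − 1)p/(1 − p)] = √(48 × 0.3/0.7) = 4.54, p = 0.00004. The mean rise is 0.3 × 1395 = 418.5 mg for b = 5, and 0.3 × 1200 = 360 mg for b = 200.

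**Probability of significance, c = 0.** If k of 49 reach 1400 mg, t = √[48k/(49 − k)]. For k = 3 this is 1.77; for k = 4 it is 2.07, above the critical value of 2.01. Four participants are enough.

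| Untreated rate | Probability of at least 4 of 49 |
|---|---|
| 30% | over 99.9% |
| 10% | 74% |
| 5% | 23% |

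**If everyone not desensitised loses the whole baseline threshold (c = −b), rate 30%.**

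| b (mg) | Mean change (mg) | t | Probability of a significant rise |
|---|---|---|---|
| 50 | 0.3 × 1350 − 0.7 × 50 = 370 | 4.00 | 99.7% |
| 200 | 0.3 × 1200 − 0.7 × 200 = 220 | 2.38 | 64% |
| 400 | 0.3 × 1000 − 0.7 × 400 = 20 | 0.22 | expected result not significant |

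**Spread baselines, by simulation.** With baselines spread over 1 to 400 mg and random change in the rest (4,000 trials per setting), 30% desensitised and no treatment:

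- Absolute change: a significant rise in essentially 100% of trials.
- Log fold change: 99-99.8% with no drift, and 76% if the rest drift down by 0.5 log units.
- Between-group t-test, with 30% in both arms: rejects in 5.1-5.5% (absolute) and 4.8-5.3% (log fold), its nominal rate.

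Varying the assumed baseline median from 20 to 150 mg gives about 97-100% for the paired test. With log-normal baselines of median 50 mg, untreated rates of 10% and 5% give 56-72% and 15-23%.

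**QoL.** No calculation applies. The 30% is a desensitisation rate and implies no QoL change. Both windows in the before-after bullet are treated periods: baseline to phase 1 for the intervention arm, and phase 1 to phase 2 for the waiting list.

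**The case against.** The strongest reply is that these percentages measure power, not error. If 30% of controls truly reach 1400 mg, the mean has changed and rejecting no change is correct. A before-after summary of the control arm even helps in reading the randomised contrast. That is right, and it is why the change belongs in the report as description. It does not make the p-value evidence of efficacy.

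Second, most of the remedy is already present. The between-group threshold test stands in the same sentence and is the only one in Table 2.3, QoL at the end of phase 1 is compared between groups, and section 9 asks for an effect size and 95% interval with every test. A 95% interval for the mean change excludes zero exactly when p < 0.05, so dropping the p-value is largely a matter of labelling. This stands too, and keeps the point small.

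Three stronger readings are tempting but unsupported:

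- A reader might infer that the QoL signed-rank test would also be significant without treatment. Nothing in the SAP gives a QoL change in untreated participants, and the windows tested are treated ones.
- A reader might infer that phase 2 efficacy is to be confirmed by a before-after p-value. Section 6 instead asks that the overall success rate lie within 10% of the phase 1 intervention rate. Section 9.2 compares the two incidences by Fisher's test, and the threshold bullet names no phase 2 window.
- A reader might infer that the main result is in doubt. The primary analysis is a between-group Fisher test, and the SAP nowhere says that efficacy will be concluded from a within-group test.

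**Conclusion.** The point holds for the within-group threshold test. On the SAP's planning rate of 30%, the test would be significant in an untreated arm of 49 in about 97-100% of trials with assumed baseline medians of 20-150 mg, so it cannot serve as an efficacy test. The figure depends on that rate and is much lower at 5-10%. It also depends on participants who are not desensitised not losing a large offsetting amount: a downward drift of 0.5 log units lowers the fold-change result to 76%, and complete loss of a 200 mg baseline lowers the absolute result to 64%. The principle does not depend on the exact figure, because any untreated change in the mean threshold has the same effect.

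For QoL only the qualitative remark stands: the test is uncontrolled and comes from unblinded participants. This is a minor fault in the labelling and interpretation of secondary analyses. It leaves the primary analysis, the between-group secondary tests and the section 6 criterion for phase 2 intact.

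**What to change.** 1. In section 9.2 and Table 2.5, replace the within-group tests of threshold and QoL by estimates of change with 95% confidence intervals, labelled descriptive and uncontrolled, without efficacy p-values. For threshold this brings section 9.2 into line with Table 2.3.
2. State that efficacy inference for threshold and QoL rests on the randomised comparison at the end of phase 1, adjusted for the baseline value of the same variable. For threshold, analyse on the log scale and state the offset used when the NOAEL is zero, since a fold change from zero is undefined. This replaces the optional wording about extending to a linear regression.

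The change costs SAP wording only and needs no new data. The downside is that before-after changes, including those in phase 2, carry no p-value. In simulation under assumed inputs, baseline adjustment of the between-group threshold comparison raised power slightly, from 83% to 86%, with type I error near 5%.
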